Research Protocol

Protocol Title:

Early Stability of Short Implants with Shallow Threads in the
Posterior Mandible: A Controlled Clinical Pilot Study.

Date: August - 19- 2025

Principal Investigator

[name]

Thesis Supervisor:

[name] [name]

(Associate Professor of Oral and Maxillofacial Surgery)

University of Science and Technology,

Yemen.

1. Background and Rationale

Patients with severely resorbed posterior mandibles face a significant challenge. While short implants (SHI, $\leq 8\text{mm}$) offer a less invasive alternative to complex bone augmentation, they are associated with a higher risk of early failure, often linked to compromised stability during the critical healing phase known as the "stability dip." This dip, a period of osteoclast-mediated resorption, creates micromotion that can disrupt osseointegration. The role of implant macrodesign, specifically shallow threads, and bone density in modulating this early stability trajectory remains unclear. This study aims to prospectively compare the early stability dynamics of short (7mm) versus standard (11mm) shallow-threaded implants to provide evidence for their use as a viable graft-less solution.

2. Study Objectives and Hypotheses

· Primary Objective:

To compare the early stability dynamics (primary stability, stability dip, and onset of secondary stability) of 7 mm short implants (SHI) versus 11 mm standard implants (SDI), both with an identical shallow-threaded macrodesign, in the non-augmented posterior mandible over 4 weeks.

· **Secondary Objective:**

To assess the effect of bone density (D2 vs. D3) on these stability parameters.

Hypotheses:

- H_01 : No significant difference in primary stability (ITV, ISQ-T0) exists between SHI and SDI.
- H_02 : No significant relationship exists between baseline ISQ and the stability dip magnitude/duration for either implant type.
- H_03 : Bone density has no differential effect on stability parameters between SHI and SDI.

3. Study Design

A prospective, controlled, non-randomized clinical pilot study employing $\geq 80\%$ split-mouth design where anatomically feasible. Implant allocation follows clinical necessity principles:

- Short Implant (SHI; 7 mm): Sites with 8–10 mm bone height above the inferior alveolar canal.

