6. Implant placement with slow manual seating. Insertion Torque Value (ITV) is recorded during the final 90° rotation.
7. SmartPeg attachment and baseline Implant Stability Quotient (ISQ) measurement using RFA (T0).
8. Closure with sutures.

· Post-Operative Care:

- Analgesics (Diclofenac) and antibiotics (Amoxicillin/Clavulanate).
- Instructions for soft diet and chlorhexidine mouth rinses.

- **Follow-up and Stability Monitoring:**

- Participants will return for ISQ measurements at the end of weeks 1, 2, 3, and 4 (T1, T2, T3, T4).
- At each visit, quadruple RFA measurements (buccal, lingual, mesial, distal) will be taken, and the mean ISQ value calculated.

8. Outcome Measures

- **Primary Stability:**

- Insertion Torque Value (ITV) in Ncm.
- Baseline ISQ value (T0).

- **Stability Dip Characteristics:**

- Dip Magnitude (Δ ISQ-min): Difference between ISQ at T0 and the lowest ISQ value (ISQ-min) recorded between T1-T4.
- Time of Dip (T-min): The week (T1-T4) at which the lowest ISQ value occurred.

- **Secondary Stability Onset:** The first timepoint where ISQ values consistently increase by ≥ 2 units from the ISQ-min.
- **Effect Modifier:** Bone density (D2 vs. D3) as a primary covariate.

9. Data Management and Statistical Analysis

- **Data Collection:**

De-identified data will be recorded on standardized Case Report Forms (CRFs) and stored in a password-protected electronic database (Excel).

- **Statistical Analysis:**

Will be performed using SPSS Statistics (v28). Analysis will include:

- Descriptive statistics for all variables.
- Paired t-tests (for bilateral cases) and independent samples t-tests (for full dataset) to compare primary stability (H_01).
- Pearson/Spearman correlation to assess the relationship between baseline ISQ and dip magnitude (H_02).
- Linear Mixed Models (LMM) to analyze longitudinal ISQ trajectories.

- Two-Way ANOVA to test the interaction effect of Implant Type and Bone Density on dip magnitude (H_03).
- A p-value of <0.05 will be considered statistically significant, with Bonferroni correction for multiple comparisons.

10. Ethical Considerations

- **Approval:**

This study has been approved by the University of Science and Technology Institutional Review Board. (IRB Approval No: **1447/0062/UREC/UST**).

- **Informed Consent:**

Written informed consent will be obtained from all participants after a detailed explanation of the study procedures, potential risks, and benefits.

· Confidentiality:

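### Section 8 assigns a dip week, and sometimes an onset of secondary stability, to implants whose ISQ never falls below T0 (minor)

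*Protocol*

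**What the plan says.** The primary objective (Section 2) compares the two implant types on "primary stability, stability dip, and onset of secondary stability". H_02 adds a duration: "No significant relationship exists between baseline ISQ and the stability dip magnitude/duration for either implant type".

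Section 8 defines the outcomes as follows.

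- Dip magnitude: "Difference between ISQ at T0 and the lowest ISQ value (ISQ-min) recorded between T1-T4".
- Dip week: "Time of Dip (T-min): The week (T1-T4) at which the lowest ISQ value occurred".
- Onset of secondary stability: "The first timepoint where ISQ values consistently increase by ≥ 2 units from the ISQ-min".

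Section 7 fixes the data behind them. Each implant has a T0 value and four later ones, and T4 is the last visit. Each value is an average over four directions: "At each visit, quadruple RFA measurements (buccal, lingual, mesial, distal) will be taken, and the mean ISQ value calculated".

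Section 9 plans "Descriptive statistics for all variables". Its named tests use primary stability, dip magnitude and the ISQ trajectory.

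**The concern.** T0 cannot be the minimum, because the minimum is sought only among T1-T4. One of those four readings is always the lowest, so the rule always returns a dip week, whether or not stability was lost. Onset is then measured from that same minimum, so an implant with a steady gain can be credited with a recovery from a loss it never had.

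T-min and onset are the only timing outcomes in Section 8, and they carry the timing part of the primary objective and of H_02. If non-dipping implants are pooled with dipping ones, a summary dip week or onset week describes two different things at once. With 10 implants per type, each such implant is 10% of its group.

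Two lesser gaps sit in the same definition. The word *consistently* is not explained. An implant whose minimum falls at T4 can have no observed onset.

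**Working it through.** **1. The definitions applied literally (no assumption about noise).** Let m be the lowest of T1-T4. Dip magnitude = T0 − m; T-min = the week of m; onset = a later reading of at least m + 2.

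| T0, T1, T2, T3, T4 | m | Magnitude | T-min | Onset |
|---|---|---|---|---|
| 70, 71, 72, 73, 74 | 71 | 70 − 71 = −1 | week 1 | first reading ≥ 73: T3 |
| 70, 70, 70, 70, 70 | 70 | 0 | tied, weeks 1-4 | none |
| 70, 66, 68, 67, 69 | 66 | 4 | week 1 | first reading ≥ 68: T2; held through T4: T4 |
| 70, 68, 66, 65, 64 | 64 | 6 | week 4 | cannot be observed |

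The first row is the core of the point: there is no fall, yet a dip week and an onset are assigned. The second shows that ties have no rule. The third and fourth show the two lesser gaps.

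**2. How often this could happen.** The protocol gives neither the noise of a visit mean nor an expected profile, so both are assumed here: independent normal noise with SD 1, 1.5 or 2 ISQ on each of T0-T4, and 1,000,000 simulated implants per cell. Brackets give the true change from T0 at T1-T4. Onset is counted when every reading from it through T4 is at least m + 2. Entries are percentages of all implants, for SD 1 / 1.5 / 2.

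| Profile | No dip (m not below T0) | No dip, yet an onset scored | Dip, onset not reached by T4 |
|---|---|---|---|
| Flat (0, 0, 0, 0) | 20.0 / 20.0 / 20.0 | 1.8 / 4.7 / 6.8 | 64.1 / 50.1 / 42.1 |
| Rising (1, 2, 3, 4) | 72.5 / 59.4 / 51.0 | 56.7 / 42.9 / 35.7 | 1.7 / 4.8 / 7.5 |
| Week-2 trough (−3, −4, −2, 0) | 0.1 / 0.8 / 2.4 | 0.0 / 0.5 / 1.6 | 4.3 / 9.0 / 11.9 |
| Week-3 trough, near recovery (−2, −3.5, −4, −1) | 0.0 / 0.6 / 1.9 | 0.0 / 0.3 / 1.1 | 14.5 / 18.5 / 19.9 |
| Week-3 trough, partial recovery (−2, −3.5, −4, −2.5) | 0.0 / 0.4 / 1.6 | 0.0 / 0.1 / 0.6 | 54.4 / 45.9 / 40.5 |

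The flat figure has an exact check. With five exchangeable readings, T0 is the lowest with probability 1/5 = 20%, whatever the SD.

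Out of 20 implants, no dip means 0.20 × 20 = 4 on a flat profile, 0.51 × 20 to 0.73 × 20 = about 10 to 15 on a rising one, and at most 0.024 × 20 = 0.5 with a true trough.

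**3. What *consistently* is worth.** Taking the first qualifying reading, rather than one held through T4, changes the onset in 0.5-7.9% of implants with a trough and in 11-16% on a flat or rising profile.

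**4. Which analyses use these outcomes.** Section 9 names t-tests on primary stability, a correlation with dip magnitude, a two-way ANOVA on dip magnitude, and a mixed model on ISQ. None takes T-min or onset as its variable. Only the descriptive summaries do.

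**The case against.** The strongest reply is that the outcome is titled as the time of a dip and listed among the dip characteristics, so it naturally concerns implants that dipped. The background section also expects a dip; where a true 4-ISQ trough exists, fewer than one implant in 20 would be affected. The signed magnitude identifies every non-dipping implant, and all five ISQ values are kept, so any rule can be applied later.

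Much of this stands and limits the size of the point. It does not remove it. The sentence in Section 8 still yields a week for every implant, and no text withholds that value from the summaries.

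A reader might infer more than the protocol supports, in four ways.

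- *That the planned tests are compromised.* They are not; none uses T-min or onset.
- *That most implants would be misclassified.* This holds only on a rising profile, which runs against the protocol's own premise of a dip.
- *That leaving* consistently *unexplained, or having no rule for a minimum at T4, is by itself a defect of the protocol.* These are largely derivation details that an analysis plan not shown here could hold. They are covered in the fix because the same sentence is being rewritten.
- *That taking the lowest of four noisy readings biases the comparison of dip size between implant types.* When noise and profile are similar in the two groups, this largely cancels, so it is no part of this point.

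**Conclusion.** The point holds in a limited form. The T-min and onset definitions lack a condition that ISQ fell below T0, and followed as written they give wrong values for implants that did not dip. This follows from the text alone and needs no assumption.

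The frequency does rest on assumptions. With noise SD of 1-2 ISQ, no dip occurs in about 20% of implants on a flat profile, 51-73% on a rising one, and 0-2.4% with a true 4-ISQ trough. In the trough case the more common problem is an onset not reached by T4 (4-55%), which makes a mean onset week among observed onsets unrepresentative.

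Only descriptive summaries are touched, though of outcomes in the primary objective. Severity is minor.

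**What to change.** Amend Section 8, before the ISQ trajectories are examined, as follows.

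1. Assign T-min and onset only when ISQ-min is below T0. Otherwise record *no dip* and keep the signed magnitude.
2. If minima tie, take the earliest week.
3. Score onset as the first reading after T-min from which every reading through T4 is at least ISQ-min + 2.
4. Report for each implant type, out of all implants, the counts *no dip*, *onset by T4* and *not reached by T4* (including T-min at T4). Do not report a mean onset week among observed onsets only.

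This adds no visits, participants or measurements and leaves the Section 9 tests as they are. It does have costs. Some implants will have no T-min or onset, and a mean onset week may not be available. The held-through-T4 rule dates some onsets later or not at all, and an onset at T4 still rests on one reading. Small noise dips still count: on a flat profile, 100% − 20% = 80% of implants would still be scored as having dipped.

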- Standard Implant (SDI; 11 mm): Sites with >10 mm bone height. Randomization is precluded on ethical grounds, as placing an SHI in a site suitable for an SDI violates the standard of care.

4. Participant Selection

· Inclusion Criteria:

- Aged 18–65 years.
- Posterior mandibular partial edentulism requiring implant placement.
- Native bone height of 8–13 mm above the inferior alveolar canal.
- Bone width ≥ 5.5 mm.

- Bone density classified as D2 (850–1250 HU) or D3 (350–850 HU) via pre-operative CBCT.
- Plaque Index ≤ 1 .
- ASA physical status I or II.
- Provides written informed consent.

- **Exclusion Criteria:**
- Absolute surgical contraindications.
- Uncontrolled diabetes (HbA1c $> 7\%$) or immunosuppression.
- History of head/neck radiation or bisphosphonate therapy.
- Active periodontitis (PPD > 5 mm) or bone pathology.
- Smoking > 10 cigarettes/day.
- Parafunctional habits.
- Previous bone grafting at the intended implant site.

5. Sample Size

The sample will consist of Ten participants receiving 20 implants (10 SHI, 10 SDI). This is a pilot feasibility sample, determined by strict eligibility criteria and a post-hoc power analysis indicating 80% power to detect a clinically significant difference in ISQ dip ($\Delta\text{ISQ} \geq 5$) with an alpha of 0.05.

6. Materials and Methods

• **Implant System:**

A tiologic TWINFIT implants (DENTAURUM GmbH). Both SHI (7mm) and SDI (11mm) share an identical design:

- 4.2mm diameter
- 5-degree taper
- Shallow threads (0.35-0.45mm),
- Sandblasted, acid-etched (SLA) surface.

· Key Equipment:

- CBCT Machine (Vatech EZ-3D) for pre-surgical planning and bone density assessment.
- Surgical motor (W&H Implantmed) with a 20:1 reduction handpiece.
- Calibrated torque wrench.
- Resonance Frequency Analysis (RFA) device (Penguin RFA) with type 4 SmartPegs.

7. Study Procedures

· Pre-Operative Phase:

1. Screening against inclusion/exclusion criteria.
2. Clinical examination and plaque index recording.
3. CBCT scan with Hounsfield Unit (HU) calibration using a hydroxyapatite phantom to determine bone density (D2/D3).
4. Obtaining written informed consent.

· Surgical Protocol:

1. Premedication: Ibuprofen 400 mg.
2. Asepsis with povidone-iodine (perioral) and chlorhexidine (intraoral).
3. Local anesthesia (2% lidocaine with 1:80,000 epinephrine).
4. Crestal incision and full-thickness flap elevation.
5. Osteotomy performed with an under-preparation protocol.

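### The H01 full-dataset t-test and the H03 two-way ANOVA have no participant term, although 20 implants sit in 10 mostly split-mouth participants

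*Protocol*

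**What the plan says.** - **Sample (Protocol section 5):** "The sample will consist of Ten participants receiving 20 implants (10 SHI, 10 SDI"), so on average two implants per participant.
- **Design (section 3):** at least 80% "split-mouth design where anatomically feasible". Eight or more of the ten participants are meant to carry one implant of each type, but this is a target.
- **Density (section 4):** an inclusion criterion reads "Bone density classified as D2" or D3 on pre-operative CBCT. Nothing fixes how the two classes fall within participants or across implant types.
- **H01 (section 2):** "No significant difference in primary stability (ITV, ISQ-T0) exists between SHI and SDI". Section 9 assigns it "Paired t-tests (for bilateral cases) and independent samples t-tests (for full dataset) to compare primary stability (H_01").
- **H03 (section 9):** "Two-Way ANOVA to test the interaction effect of Implant Type and Bone Density on dip magnitude (H_03"). No other H03 test is named.
- **Mixed model (section 9):** "Linear Mixed Models (LMM) to analyze longitudinal ISQ trajectories". It is not tied to H01 or H03, and a trajectory model cannot cover ITV, which is measured once, at placement.
- **Multiplicity (section 9):** a 0.05 threshold "with Bonferroni correction for multiple comparisons", with no set of comparisons named.

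**The concern.** Two implants in one mouth share bone, healing and host factors, so their measurements are likely to be correlated. The paired test shows that the plan recognises this. The full dataset, however, contains the pairs, and the independent test treats them as unrelated. The two-factor ANOVA does the same.

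An analysis that ignores clustering uses the wrong variance for its contrast. Whether that variance is too large or too small depends on whether the contrast compares implants mainly within or between participants. For H01 a valid paired test stands beside the faulty one, so what is at stake is power, the data from non-bilateral participants, and two answers that may differ. For H03 no second test is named, so the true level of the only test depends on a density layout known only after enrolment.

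**Working it through.** **Inputs.** From the protocol: 10 participants, 20 implants, 10 of each type, at least 8 of 10 split-mouth as a target, level 0.05 (taken as two-sided). Assumed, because the protocol gives none: within-participant correlation ρ from 0.1 to 0.7, equal variance σ², and the density layouts below.

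**The plan's own figure.** Section 5 claims 80% power for a difference of 5 ISQ in dip, without an SD. With 10 per type, an independent two-sided t-test needs a standardised difference of 1.325, so SD = 5/1.325 = 3.77. A paired test on 10 pairs needs 0.996, so the SD of differences = 5/0.996 = 5.02. The claim can be neither confirmed nor refuted. The SD of 3.77 serves below only as an illustration, since it concerns dip and not ISQ-T0.

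**H01, variance.** Let p participants be split-mouth and the rest divide evenly into two-SHI and two-SDI participants. Then

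Var(difference in means) = 0.2σ²[1 + ρ(1 − p/5)].

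The independent test works with about 0.2σ². The factor is 1 − ρ for p = 10 and 1 − 0.6ρ for p = 8. Both are below 1, so the test is conservative. At p = 4 it is 1 + 0.2ρ and the test turns liberal, but that is half the split-mouth target.

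**H01, simulated type I error** (nominal 5%):

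| Layout | ρ = 0.1 | ρ = 0.7 |
|---|---|---|
| 10 pairs | 4.0% | 0.2% |
| 8 pairs + one two-SHI + one two-SDI | 4.4% | 1.1% |

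The paired t-test stays at about 5%.

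**H01, power** (5 ISQ, SD 3.77, ρ = 0.5):

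| Layout | Independent | Paired | Mixed model, type only |
|---|---|---|---|
| 10 pairs | 87% | 96% | 96% |
| 8 + 2 | 84% | 89% | 93% |

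The independent and paired tests reach different conclusions in 10% (10 pairs) to 15% (8 + 2) of these trials. At ρ = 0 with 8 + 2 the order reverses: 80% for the independent test against 62% for the paired test, which loses two participants.

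**H03, variance.** The interaction contrast is (SHI,D2 − SHI,D3) − (SDI,D2 − SDI,D3). Take 10 pairs, and call a participant discordant if one site is D2 and the other D3. If k are discordant, split evenly by direction, and the rest divide evenly between D2 and D3, every cell holds 5 implants. The variance is then 0.8σ²[1 + ρ(k − 5)/5].

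Direction matters as well. With six discordant, all SHI-D2/SDI-D3, and two shared in each class, the cells hold 8, 2, 2 and 8:
- variance terms: 8/64 + 2/4 + 2/4 + 8/64 = 1.25
- four shared participants: 4 × 2ρ × (1/8)(−1/2) = −0.5ρ
- six discordant participants: 6 × 2ρ/64 = 0.1875ρ
- total: σ²(1.25 − 0.3125ρ) = 1.25σ²(1 − 0.25ρ)

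The factor falls below 1, against 1 + 0.2ρ for the 3+3 split. Eight in one direction (cells 9, 1, 1, 9) gives 20/9 − 4ρ/9 + 16ρ/81 = (20/9)(1 − ρ/9), also below 1.

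**H03, simulated type I error of the ANOVA interaction** (10 pairs):

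| Density layout | Variance factor | ρ = 0.1 | ρ = 0.7 |
|---|---|---|---|
| all shared, 5 D2 and 5 D3 | 1 − ρ | 4.0% | 0.2% |
| six discordant, 3+3 | 1 + 0.2ρ | 5.2% | 6.4% |
| six discordant, 6+0 | 1 − 0.25ρ | 4.8% | 2.9% |
| eight discordant, 4+4 | 1 + 0.6ρ | 5.6% | 9.7% |
| eight discordant, 8+0 | 1 − ρ/9 | 4.8% | 3.9% |
| ten discordant, 5+5 (extreme) | 1 + ρ | 6.1% | 13.2% |

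A rerun of both type I error tables agreed to within about 0.1 percentage point.

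**The case against.** **The usual inference, that ignoring clustering inflates false positives.** A reader might draw it here. The documents do not support it: near the split-mouth target the H01 test errs on the safe side, and the H03 test can err either way.

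**The 13.2% as the expected H03 error.** That figure needs every participant to be discordant, an even split by direction and a correlation of 0.7. Nothing in the protocol makes that likely. Nor does the number of discordant participants settle the matter, because six or eight discordant in one direction leave the ANOVA conservative.

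**Low correlation.** Dip is a change from each implant's own T0, so a stable participant-level shift in ISQ cancels, and the correlation for dip may be small. This stands, and it is why the range starts at 0.1, where the errors are modest.

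**The H01 harm is small.** This largely stands. A valid test is already planned. Even taking whichever H01 test is significant gives 5.0% to 6.8% at correlations 0.3 to 0.7 (10 pairs and 8 + 2), or 2.5% to 3.4% with Bonferroni over the two tests. The disagreement figures rest on an SD borrowed from another endpoint, and none can be given for ITV.

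**The missing order between the two H01 tests belongs in the SAP.** Fair, and that alone is not the point. The point is that the protocol itself prescribes two analyses that ignore pairing. Reading the independent test as meant for the non-bilateral remainder does not help, since section 9 applies it to the full dataset.

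**It is a pilot.** Section 9 still sets a formal significance threshold for these hypotheses.

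**Conclusion.** The point holds in a limited form and should be fixed. Two analyses prescribed in section 9 omit the participant, so their true level is not the nominal 5% unless implants in one mouth are uncorrelated or the layout happens to balance. For H01 the independent test is conservative at the planned layout (4.4% down to 0.2%). The cost is mainly power when correlation is moderate or high, and possible conflict with the paired test, which drops non-bilateral participants. H03 is the weightier part: its only named test runs from 0.2% to 9.7% outside the extreme layout. Its direction cannot be known before the densities and their pairing with implant type are known.

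That the participant term is missing is certain from the text. The sizes rest on assumed correlations, equal variances and illustrative layouts.

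**What to change.** **H01, separately for ITV and ISQ-T0:** replace the independent t-test with a linear mixed model on all implants, with implant type as the fixed effect, a random participant intercept and Kenward-Roger degrees of freedom. Name its type contrast as the deciding test. Keep the paired t-test on bilateral cases as a sensitivity check.

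**H03:** add a random participant intercept to the type-by-density interaction model, with Kenward-Roger degrees of freedom. Report the interaction as not estimable if a type-by-density cell is empty.

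**Cost:** wording and slightly more analysis work. No new data are needed, and section 9 already plans mixed models in SPSS. The small-sample degrees of freedom are approximate. In simulations at correlations 0.3 to 0.7 (40,000 runs per cell), Kenward-Roger gave a type I error of 4.8% to 5.5% for H01 and 4.2% to 5.5% for H03. If only Satterthwaite is available, the ranges were 4.8% to 7.1% and 4.2% to 7.9%.

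The change does not rescue H03 as a confirmatory test. For an illustrative 5 ISQ interaction (SD 3.77, correlation 0.5), power is 46% with all densities shared 5/5, against 23% for the ANOVA. With four discordant participants it is 35% against 28%.

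### H_01 is tested only by t-tests that cannot adjust for bone density, although bone height decides which implant a site receives, so a difference in primary stability cannot be read as an effect of length

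*Protocol*

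**What the plan says.** - **Allocation (Section 3).** The design is described as "A prospective, controlled, non-randomized clinical pilot study employing" a split-mouth layout in at least 80% where anatomy allows. The 7 mm implant (SHI) goes to "Sites with 8–10 mm bone height above the inferior alveolar canal" and the 11 mm implant (SDI) to "Sites with >10 mm bone height". Randomisation is ruled out because "placing an SHI in a site suitable for an SDI violates the standard of care".
- **Size (Section 5).** "Ten participants receiving 20 implants (10 SHI, 10 SDI".
- **Status of density (Section 8).** Under the label of effect modifier: "Bone density (D2 vs. D3) as a primary covariate".
- **H_01 (Sections 2 and 9).** The hypothesis of no difference in insertion torque (ITV) and ISQ at T0 is tested by paired t-tests in bilateral cases and "independent samples t-tests (for full dataset) to compare primary stability (H_01". No other analysis in Section 9 is tied to H_01.
- **Other outcomes (Section 9).** Dip magnitude is analysed by a two-way ANOVA with implant type and bone density. ISQ trajectories are analysed by linear mixed models whose terms are not listed.

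**The concern.** In a non-randomised comparison, adjustment for known site differences is the main protection against reading a site effect as a treatment effect. The protocol names its leading covariate and then assigns to its first hypothesis two tests that have no place for it. Section 9 does not leave this open, because it names the tests.

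The primary objective compares two lengths with the same macrodesign, which invites the reader to credit any difference to length. A finding of no difference is just as ambiguous, since a site difference could mask a length effect. That matters here because the rationale in Section 1 looks for evidence that short implants are a workable alternative to grafting.

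The full-dataset t-test adds a second weakness: it ignores that most implants share a patient with another implant in the study.

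**Working it through.** **1. The plan's own figure.** The only quantitative statement is a "post-hoc power analysis indicating 80% power to detect a clinically significant difference in ISQ dip" of at least 5 units at alpha 0.05. It concerns dip, not H_01, and no SD is given, so it cannot be reproduced. Solving backwards with the noncentral t (10 v 10, two-sided), 80% power at a difference of 5 implies SD = 3.77. That value is borrowed below only to set a scale.

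**2. Which adjustments are possible.**
- Density: D2 and D3 sites are eligible for both implant types, so density can be adjusted for.
- Height: 8–10 mm always means SHI and above 10 mm always means SDI. The types share no height, so no covariate can separate height from length without extrapolation.

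**3. Bias from omitting density.** Let g be the D2-minus-D3 effect on the outcome. With no true length effect, the expected SHI-SDI difference is g × (D2 share in SHI − D2 share in SDI). The formula is the same for the paired test, since the mean of the within-patient differences carries the same term. Example: g = 5 with 7/10 v 3/10 gives 5 × 0.4 = 2.0.

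**4. Simulation.** 20,000 runs, 10 v 10, no true length effect, implants independent. Assumptions not in the documents: SD 3.77 within density class, g = 3, 5 or 8, and the D2 counts shown. Each cell lists results for g = 3 / 5 / 8.

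| D2 sites, SHI v SDI | False difference | Rejection, t-test | Rejection, density in model | SE factor |
|---|---|---|---|---|
| 5 v 5 | 0 / 0 / 0 | 3.2% / 1.8% / 0.4% | 4.7% / 5.0% / 5.2% | 1.00 |
| 6 v 4 | 0.6 / 1.0 / 1.6 | 4.9% / 4.0% / 2.6% | 5.1% / 4.8% / 5.2% | 1.02 |
| 7 v 3 | 1.2 / 2.0 / 3.2 | 8.2% / 11.8% / 15.7% | 4.9% / 5.2% / 5.1% | 1.09 |
| 8 v 2 | 1.8 / 3.0 / 4.8 | 14.7% / 29.3% / 51.9% | 5.0% / 5.1% / 5.0% | 1.25 |

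The SE factor is 1/√(1 − r²), where r is the correlation of type with density. With half the sites D2 overall, r equals the difference in shares: 1/√(1 − 0.4²) = 1.09 and 1/√(1 − 0.6²) = 1.25.

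**5. Limit of the SE factor.** It assumes independent implants. In a purely within-patient analysis of 10 pairs the factor can be larger. If all discordant pairs at 7 v 3 point the same way, four pairs differ by 1 and six by 0. The mean is 0.4 and the sum of squares is 4 − 10 × 0.16 = 2.4. The factor is then √(1 + 10 × 0.16/2.4) = 1.29. At 8 v 2 (six pairs differ by 1, four by 0) the sum of squares is 6 − 10 × 0.36 = 2.4 and the factor is √(1 + 10 × 0.36/2.4) = 1.58.

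**6. Ignoring the patient.** If 80% refers to participants, at least 0.8 × 10 = 8 are split-mouth. For n patients with one implant of each type and within-patient correlation ρ, the variance of the difference in means is 2σ²(1 − ρ)/n, but the independent t-test uses 2σ²/n. At an assumed ρ = 0.5 it overstates the SE by 1/√0.5 = 1.41. For such patients the error is therefore conservative: it costs power and favours a finding of no difference.

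**The case against.** The strongest reply has five parts.

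- **This is an open, non-randomised pilot.** The protocol declares the allocation rule and gives an ethical reason. That stands, but it does not justify an H_01 test without the declared covariate.
- **Pairing covers most patients.** The paired t-test removes patient-level differences. It does not remove differences between a patient's two sites, which must differ in height by the allocation rule and may differ in density.
- **Density is not ignored.** A reader might infer that every SHI-SDI comparison is unadjusted. The documents do not support that: the dip ANOVA contains density, and the trajectory model's terms may be in an analysis plan not shown. The point is confined to ITV and ISQ at T0.
- **No imbalance is shown.** A reader might infer that the arms do differ in density. Nothing in the protocol shows this; non-random allocation only makes it possible. Nor is chance imbalance a bias by itself, because random scatter in density is already part of the t-test's standard error. The bias that matters would come from a systematic link between bone height and density, which the documents neither state nor exclude.
- **The 5-unit threshold belongs to dip.** The protocol gives no threshold for ISQ at T0 or for ITV, so the false differences above should not be judged against it.

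**Conclusion.** The point holds for H_01. Section 8 names a covariate that the H_01 tests in Section 9 cannot use, in a comparison where site anatomy decides the implant. The full-dataset test also ignores the patient.

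The size depends on an imbalance that cannot be known in advance. Under the assumptions above, the false difference runs from 0 (5 v 5) to 4.8 units (8 v 2, g = 8), and the t-test's rejection rate from 0.4% to 52% against a nominal 5%. With density in the model, the bias is about zero and the rate about 5% throughout. The SD, g and the D2 counts are all assumed; the SD comes from the power statement for dip. For ITV only the bias formula carries over directly, with g in Ncm.

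A reader might also infer that the adjusted contrast would be an effect of length. It would not: height stratum and length coincide, so the wording of the objective must change as well. For a pilot this is worth correcting before analysis, but it is no reason to doubt the study as a whole.

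**What to change.** **Section 9.** Take the SHI-SDI contrast for ITV and for ISQ at T0 from a linear mixed model with implant type, site bone density (D2/D3, or the HU already measured on CBCT) and a patient random effect. State in advance which form of density is used. Keep the paired and independent t-tests as descriptive.

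**Section 2.** State that the comparison is of SHI at 8–10 mm sites with SDI at sites above 10 mm, that length cannot be separated from bone-height stratum, and that differences will not be attributed to length alone.

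**Cost.** No new data: density is recorded for eligibility. The density term takes one degree of freedom. The SE rises if density is imbalanced: about 9% at 7 v 3 and 25% at 8 v 2 with independent implants, and possibly more when the contrast is mainly within patients. With ten patients, the patient variance will be estimated imprecisely. The claim becomes narrower.
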